6.7 Registry Management

AbbVie, working in cooperation with United BioSource Corporation (UBC), will manage the registry, collect all registry information via eCRFs and PROs, if applicable, and complete all statistical analyses.

7.0 Adverse Events/Adverse Event Reporting

The physician will monitor each patient for SAEs and evidence of pre-defined AEs of Special Interest on a routine basis throughout the registry.

7.1 Definitions

7.1.1 Adverse Event

An AE is defined as any untoward medical occurrence that occurs during treatment in a patient, but does not necessarily have a causal relationship with their treatment. An AE can therefore be any unfavorable and unintended sign (including an abnormal laboratory finding), symptom, or disease temporally associated with the use of a medicinal product, whether or not the event is considered causally related to the use of the product.

Such an event can result from use of the drug as stipulated in the labeling, as well as from accidental or intentional overdose, drug abuse, or drug withdrawal. Any worsening of a pre-existing condition or illness is considered an AE.

An elective surgery/procedure scheduled to occur during a registry will not be considered an AE if the surgery/procedure is being performed for a pre-existing condition and the surgery/procedure has been planned prior to registry entry. However, if the pre-existing

condition deteriorates unexpectedly during the registry (e.g., surgery performed earlier than planned), then the deterioration of the condition for which the elective surgery/procedure is being done will be considered an AE.

7.1.2 Adverse Events of Special Interest

Table 2. AEs of Special Interest for This Registry

Serious and non-serious opportunistic infections, including the following bacterial, fungal, viral and parasitic infections: Aspergillus, Blastomyces, Candida, Coccidioides, Cryptococcal, Cytomegalovirus, Histoplasma, Listeria, Nocardia, Paracoccidioides, Pneumocystis, Toxoplasma, Tuberculosis, Herpes, Bacillary angiomatosis, Mucormycosis, Progressive Vaccinia, Zygomycosis, BK virus, and JC virus

L	y	m	ıp	h	O.	m	ıa

Hepatosplenic T-cell lymphoma

Leukemia

Non-melanoma skin cancer (NMSC)

Other malignancies (except lymphoma, leukemia and NMSC)

Immune reactions including lupus, lupus-like reactions, and severe allergic reactions

Congestive heart failure (CHF)

Cerebrovascular accident (CVA)

Myocardial infarction (MI)

CNS demyelinating disorders (including MS and Guillain-Barré syndrome)

Hepatic events that are serious or lead to permanent discontinuation of HUMIRA (e.g., persistent liver function test abnormalities, acute liver failure and other serious hepatic events)

Hematologic events that are serious or lead to permanent discontinuation of HUMIRA (e.g., aplastic anemia, Granulocytopenia, Granulocyte Maturation Arrest, Leukopenia, Neutropenia, Pancytopenia and Thrombocytopenia)

Worsening of Psoriasis

Vasculitis

Diverticulitis

Intestinal perforation

In addition, to the SAEs and AEs of Special Interest (Table 2), AEs that lead to permanent discontinuation of HUMIRA® will be collected.

Psoriasis HUMIRA® Registry

For patients participating in the direct to HCP process in addition to surgeries, hospitalizations, deaths, and the events listed as AEs of Special Interest (Table 2), AEs of Special Interest that lead to permanent discontinuation of HUMIRA® will be collected.

During the course of the registry, additional AEs of Special Interest may be identified by AbbVie. Updates to the AEs of Special Interest will be maintained and collected through the eCRF system. Sites will be trained on all updates to the eCRF system.

The physician will assess and record any additional information on the AEs of Special Interest in detail on the AE of Special Interest eCRF.

The physician will assess all reported AEs for seriousness and follow the requirements/timelines for reporting any AE that fulfills the criteria of an SAE, as defined in Section 7.1.3.

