7.1.3 Serious Adverse Events

If an AE (not limited to AEs of Special Interest) meets any of the following criteria, it is to be reported to AbbVie as a SAE within 24 hours of the site being made aware of the event.

Death of Patient	An event that results in the death of a patient.
Life-Threatening	An event that, in the opinion of the investigator, would have resulted in immediate fatality if medical intervention had not been taken. This does not include an event that would have been fatal if it had occurred in a more severe form.
Hospitalization	An event that results in an admission to the hospital for any length of time. This does not include an emergency room visit or admission to an outpatient facility.
Prolongation of Hospitalization	An event that occurs while the patient is hospitalized and prolongs the patient's hospital stay.
Congenital Anomaly	An anomaly detected at or after birth, or any anomaly that results in fetal loss.

Obvie HUMIRA® (adalimumab) P10-023 Protocol Amendment 3 Psoriasis HUMIRA® Registry

Persistent or **Significant** Disability/Incapacity An event that results in a condition that substantially interferes with the activities of daily living of a patient. Disability is not intended to include experiences of relatively minor medical significance such as headache, nausea, vomiting, diarrhea, influenza, and accidental trauma (e.g., sprained ankle).

Important Medical Event Requiring Medical or Surgical Intervention to Prevent Serious Outcome

An important medical event that may not be immediately life-threatening or result in death or hospitalization, but based on medical judgment may jeopardize the patient and may require medical or surgical intervention to prevent any of the outcomes listed above (i.e., death of patient, life-threatening, hospitalization, prolongation of hospitalization, congenital anomaly, or persistent or significant disability/incapacity). Examples of such events include allergic bronchospasm requiring intensive treatment in an emergency room or at home, blood dyscrasias or convulsions that do not result in inpatient hospitalization, or the development of drug dependency or drug abuse.

Spontaneous Abortion

Miscarriage experienced by patient.

Elective Abortion

Elective abortion performed on patient.

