10.2 Demographics and Registry Enrollment Characteristics

Demographics and baseline characteristics will be summarized for the All Treated Patient Population, the New Prescription Patient Population, and the Intermittent Treatment Population. Descriptive statistics will be presented. Number of patients with non-missing values, mean, and standard deviation will be provided for continuous variables. Counts and percentages will be provided for categorical variables. The number and percentage of patients that discontinue from the registry will be summarized, overall and by reason for discontinuation. Duration of observation in the registry and total duration of treatment will be summarized as follows:

Duration of observation in the registry is defined from the first day in the registry (enrollment visit or date of informed consent, up to the end-of-registry (as defined in Section 12.0).

The duration of treatment in the registry (registry exposure) is defined from the first dose of HUMIRA® in the registry to 14 days after the last dose of HUMIRA® excluding total days of any treatment interruptions.

Total duration of treatment (total exposure) is defined from the first recorded dose of HUMIRA® (initial dose) to 14 days after the last dose of HUMIRA® excluding total days of any treatment interruptions.

Time to observational and treatment discontinuation will also be presented as Kaplan-Meier (KM) curves.

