10.3.1 Analysis of Observational AEs

The number and percent of patients experiencing SAEs, AEs of Special Interest and AEs that lead to permanent discontinuation of HUMIRA® during the registry, regardless of whether the AEs are reported during or after the HUMIRA® treatment, will be tabulated by body system and Medical Dictionary for Drug Regulatory Activities (MedDRA) preferred term. Rates (event per 100 patient-year of observation) of SAEs and AEs of Special Interest and the 95% confidence interval will be provided. The analysis will be performed using data from first day in the registry to the date of last contact for the All Treated Patient Population. The last contact date is defined as the last date of registry or direct to HCP process participation, whichever occurs later.

Standardized incidence ratios (SIRs) will be used to compare the rates of events in this registry to the general population.

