10.3.2 Analysis of Treatment-Emergent AEs

Registry Treatment-emergent SAEs, AEs of Special Interest and AEs that lead to permanent discontinuation of HUMIRA® and All Treatment-emergent SAEs, AEs of Special Interest and AEs that lead to permanent discontinuation of HUMIRA® will be summarized.

Registry Treatment-emergent AEs includes AEs occurring from the first day in the registry to 70 days after the last dose of HUMIRA® excluding:

- 1. AEs occurring during TI which are more than 70 days after the last dose of HUMIRA[®] prior to the TI.
- 2. AEs occurring on or after the first day of the registry, but before the date of the first dose of HUMIRA[®].

All Treatment-emergent AEs include AEs occurring from the first recorded dose of HUMIRA® (i.e., the initial dose) up to 70 days after the last dose of HUMIRA® (excluding AEs during TI which are more than 70 days after the last dose of HUMIRA® prior to TI). For patients enrolled from a prior HUMIRA® study or who initiated commercial HUMIRA® therapy before entering the registry, the summaries will include the events reported during their participation in the previous study, any events reported by retrospective data collection, and any events reported during this registry.

The number and percentage of patients experiencing treatment-emergent SAEs, AEs of Special Interest and AEs that lead to permanent discontinuation of HUMIRA® will be tabulated by body system and MedDRA® preferred term. Rates (event per 100 patient-years of exposure to HUMIRA®, defined in Section 10.2) of SAEs, AEs of Special Interest and AEs that lead to permanent discontinuation of HUMIRA® and the 95% confidence interval will be provided.

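### If an AESI is added while the registry runs and earlier events are not back-collected, the rate of its non-serious, non-discontinuing events is understated, because the denominator still starts at the first registry day or first dose

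*Protocol*

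**What the plan says.** **Open list.** Section 7.1.2 follows Table 2 with "During the course of the registry, additional AEs of Special Interest may be identified by AbbVie", and then "Updates to the AEs of Special Interest will be maintained and collected through the eCRF system". It gives no rule for recovering events that occurred before the update.

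**What is collected.** Sections 7.1.2 and 7.4 limit collection during registry participation to SAEs, AESIs and AEs that end treatment permanently. Section 7.1.3 captures serious events whatever the term: "If an AE (not limited to AEs of Special Interest) meets any of the following criteria". Sections 6.5 and 6.5.3 describe retrospective collection at enrolment only, back to the first commercial dose.

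**Start of the clocks.**
- Observational rates, Section 10.3.1: "Rates (event per 100 patient-year of observation) of SAEs and AEs of Special Interest and the 95% confidence interval will be provided". The data window is "using data from first day in the registry to the date of last contact for the All Treated Patient Population".
- Observation time, Section 10.2: "Duration of observation in the registry is defined from the first day in the registry".
- Section 10.3.4 uses the same first-day start, without the direct-to-HCP process.
- Treatment-emergent rates, Section 10.3.2, are per "event per 100 patient-years of exposure to HUMIRA®, defined in Section 10.2". That exposure starts at the first registry dose or the first recorded dose.

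None of these sections makes an exception for a term added later.

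**The concern.** A rate is interpretable only if an event occurring in any part of the denominator could have entered the numerator. For an added term, a non-serious event that did not end treatment had no place in data collection before the update, yet the patient-years before the update are counted. The rate comes out too low.

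Safety is the primary objective, and AESI rates are among its main outputs. A term would plausibly be added because a concern had emerged, and this error would then push its rate toward reassurance. The error is systematic, so the planned 95% confidence interval does not reflect it. A rate that pools AESIs across terms would also rise after an addition with no change in risk.

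**Working it through.** **Inputs from the protocol.** Section 10.6 states 40% patient-year attrition over ten years: 5,000 × 10 × 0.6 = 30,000 PY and 6,000 × 10 × 0.6 = 36,000 PY. Both stated totals reproduce, and the mean is 6 PY per patient.

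**Assumptions, not in the protocol.** Loss occurs at a constant rate h. Enrolment is uniform over A years, with A = 2 or 5. The term is added T years after the first enrolment. True risk is constant.

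**Step 1, attrition rate.** Solve (1 − exp(−10h))/h = 6, which gives h = 0.1126 per year. Check: (1 − exp(−1.126))/0.1126 = 0.676/0.1126 = 6.0.

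**Step 2, share p of final patient-years accrued before the addition.**
- For T ≥ A: p = [1 − exp(−hT) × (exp(hA) − 1)/(hA)] / (6h)
- For T < A: p = [T/h − (1 − exp(−hT))/h²] / (6A)

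Examples:
- T = 6, A = 2: [1 − 0.509 × 1.122] / 0.676 = 0.635
- T = 2, A = 5: [17.76 − 15.90] / 30 = 0.062

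| Term added at | Enrolment over 2 years | Enrolment over 5 years |
|---|---|---|
| Year 2 | 0.155 | 0.062 |
| Year 4 | 0.422 | 0.231 |
| Year 6 | 0.635 | 0.469 |
| Year 8 | 0.806 | 0.673 |

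**Step 3, effect on the rate.** Let s be the fraction of the term's events already captured as SAEs or discontinuation AEs. Then reported rate / true rate = s + (1 − s)(1 − p).
- s = 0, year-6 addition: 1 − 0.635 = 0.365 to 1 − 0.469 = 0.531, an understatement of 47-64%.
- s = 0.5, year-6 addition: 0.5 + 0.5 × 0.365 = 0.68 to 0.5 + 0.5 × 0.531 = 0.77.
- s = 1: 1.00, no bias.

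The table is on the observation clock. The mechanism is the same on the exposure clocks, but the shares would differ.

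**Step 4, a pooled rate.** For illustration, assume 2.0 per 100 PY for listed AESIs, 1.0 per 100 PY for a wholly non-serious term added at year 5, and enrolment over 5 years. The cumulative pooled rate is 2.00 at year 5, 2.26 at year 6, 2.58 at year 10 and 2.65 at the end, with constant true risk.

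**The case against.** Several points on the other side have force.

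- **Contingent.** The protocol says only that terms may be added. It names no term or date. This stands: without an addition there is no bias.
- **Back-collection is not forbidden.** Section 6.5 allows safety information to be captured at any time, and the Section 7.4 reporting window from the first commercial dose could be read to require recovery of earlier events. This stands as a possible reading, so the point is conditional. The only retrospective procedure actually described, however, is at enrolment.
- **The SAP could set term-specific risk time.** It could, but the protocol itself fixes the numerator, the denominator and their start dates without exception. Followed as written, those rules give the biased rate, so this is more than missing detail.
- **Much is captured anyway.** All SAEs and all treatment-ending AEs are recorded during registry participation. An added term of the kind Table 2 uses for hepatic and hematologic events (serious or treatment-ending) would be essentially unbiased there. This stands.

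A reader might infer that every AESI rate rests on observation time from the first registry day. It does not: Section 10.3.2 and the first rate in Section 10.3.3 use exposure time. A reader might also infer that the overall AESI rate must rise over calendar time or time on drug. The protocol does not clearly define a single pooled AESI rate, plans no AESI rates by calendar year in Sections 10.3.1, 10.3.2 or 10.3.4, and says in Section 10.5 only that interim reports are annual. The drift applies only if terms are pooled or reports are compared.

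**Conclusion.** The point holds in conditional form. If an AESI is added and earlier events are not back-collected, the rate of its non-serious, non-discontinuing events is understated by the share of patient-years accrued before the addition: about 6-16% at year 2, 23-42% at year 4, 47-64% at year 6 and 67-81% at year 8. The ranges rest on assumed addition dates, assumed uniform enrolment over 2 to 5 years and constant-rate attrition matched to the protocol's 40%. The term's overall rate is understated by less, according to how many of its events are serious or end treatment.

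It would be wrong to read this as a threat to the lymphoma objective or to the sample size. Lymphoma and the other existing Table 2 terms are unaffected, as are patients enrolled after the addition. Serious events are safe only during registry participation. In the direct-to-HCP process, Section 6.5 places SAEs outside the questionnaire beyond the protocol, so a serious event of a not-yet-listed type without hospitalization, surgery or death could be missed there.

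**What to change.** In Sections 10.3.1, 10.3.2 and 10.3.4, state for any AESI added after the first enrolment:

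1. Events and patient-years both start at the later of the usual start and the date the term became active in the eCRF. For direct-to-HCP time, use the date it became active in the HCP questionnaire. The usual start may be kept if earlier events are back-collected for all enrolled patients.
2. Any longer-window rate for that term covers serious events only and excludes direct-to-HCP time before the term was on the questionnaire.
3. Any AESI rate pooled across terms, and any comparison between interim reports, uses the original Table 2 list.

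The cost is analysis wording and an activation date per added term for the eCRF and, where used, the HCP questionnaire. No new data collection is needed unless back-collection is chosen. The downside is fewer patient-years and wider confidence intervals for added terms: under the assumptions above, a year-6 addition would keep about 36-53% of the patient-years.

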7.1.3 Serious Adverse Events

If an AE (not limited to AEs of Special Interest) meets any of the following criteria, it is to be reported to AbbVie as a SAE within 24 hours of the site being made aware of the event.

Death of Patient	An event that results in the death of a patient.
Life-Threatening	An event that, in the opinion of the investigator, would have resulted in immediate fatality if medical intervention had not been taken. This does not include an event that would have been fatal if it had occurred in a more severe form.
Hospitalization	An event that results in an admission to the hospital for any length of time. This does not include an emergency room visit or admission to an outpatient facility.
Prolongation of Hospitalization	An event that occurs while the patient is hospitalized and prolongs the patient's hospital stay.
Congenital Anomaly	An anomaly detected at or after birth, or any anomaly that results in fetal loss.

Obvie HUMIRA® (adalimumab) P10-023 Protocol Amendment 3 Psoriasis HUMIRA® Registry

Persistent or **Significant** Disability/Incapacity An event that results in a condition that substantially interferes with the activities of daily living of a patient. Disability is not intended to include experiences of relatively minor medical significance such as headache, nausea, vomiting, diarrhea, influenza, and accidental trauma (e.g., sprained ankle).

Important Medical Event Requiring Medical or Surgical Intervention to Prevent Serious Outcome

An important medical event that may not be immediately life-threatening or result in death or hospitalization, but based on medical judgment may jeopardize the patient and may require medical or surgical intervention to prevent any of the outcomes listed above (i.e., death of patient, life-threatening, hospitalization, prolongation of hospitalization, congenital anomaly, or persistent or significant disability/incapacity). Examples of such events include allergic bronchospasm requiring intensive treatment in an emergency room or at home, blood dyscrasias or convulsions that do not result in inpatient hospitalization, or the development of drug dependency or drug abuse.

Spontaneous Abortion

Miscarriage experienced by patient.

Elective Abortion

Elective abortion performed on patient.

The physician will assess and record any AE of Special Interest and/or SAE in detail on the Adverse Event eCRF, including the date and time of onset, description, severity, time course, duration and outcome, relationship of the AE to drug, information specific to the event, final diagnosis/syndrome (if known), and any action(s) taken. For all AEs of Special Interest, the physician must pursue and obtain all the above-mentioned information in order to adequately determine the outcome of the AE and to assess whether it meets the criteria for classification as an SAE as well as to determine a causal relationship. Follow-up safety queries will be issued to sites three times and considered closed after the next scheduled quarterly monitor contact per approval of the medical monitor listed in Section 1.0. In the event of a death, follow-up will include an autopsy report, if available, and a death certificate.

Obvie HUMIRA® (adalimumab) P10-023 Protocol Amendment 3 Psoriasis HUMIRA® Registry

7.2 Severity

The physician will use the following definitions to rate the severity for any AE of Special Interest being collected as an endpoint/data point in the registry and for all SAEs.

Mild The adverse event is transient and easily tolerated by the patient.

Moderate The adverse event causes the patient discomfort and interrupts

the patient's usual activities.

The adverse event causes considerable interference with the Severe

patient's usual activities and may be incapacitating or

life-threatening.

7.3 **Relationship to Pharmaceutical Product**

The physician will use the following definitions for any AE of Special Interest being collected as an endpoint/datapoint in the registry and for all SAEs, to assess the relationship of the AE to the use of HUMIRA®. For all SAEs and AEs of Special Interest with a possible or probable causal relationship to HUMIRA® treatment, follow-up by the physician is required until the event or its sequelae resolve or stabilize at a level acceptable to the physician:

Probably Related An adverse event has a strong temporal relationship to

pharmaceutical product or recurs on re-challenge and another

cause of event is unlikely or significantly less likely.

Possibly Related An adverse event has a strong temporal relationship to the

pharmaceutical product and another cause of event is equally or

less likely compared to the potential relationship to drug.

Probably Not

An adverse event has little or no temporal relationship to the Related

pharmaceutical product and/or a more likely other cause of

event exists.

Not Related An adverse event is due to an underlying or concurrent illness or

> effect of another drug and is not related to the pharmaceutical product (e.g., has no temporal relationship to drug or has a much

more likely other cause of event).

If an Investigator's opinion of possibly, probably not, or not related to pharmaceutical product is given, an Other cause of event must be provided by the Investigator for the SAE.

7.4 Adverse Event Collection Period

SAEs, AEs of Special Interest, and AEs that lead to permanent registry HUMIRA[®] discontinuation will be reported to AbbVie starting from the first commercial dose of HUMIRA[®] or when the initial informed consent is signed, (whichever date is earlier), throughout the patient's participation in the registry, or direct to HCP process, until satisfactory resolution or for 70 days after their last dose of registry drug (whichever period is longer) to further evaluate safety.

Follow-up received on ongoing SAEs and/or AESIs post registry conclusion should be reported using standard Post-Marketing Reporting.

[figure not shown]
For patients participating in the direct to HCP process, surgeries, hospitalizations, deaths, events listed as AEs of Special Interest (Table 2), and AEs of Special Interest that lead to permanent discontinuation of HUMIRA® will be collected.

In the event HUMIRA[®] therapy is interrupted (Section 10.1), the patient will remain in the registry and continue to be monitored during the treatment interruption for SAEs and AEs of Special Interest and will be questioned for changes in their psoriasis medications and medical history of the event at their registry visits. If treatment with HUMIRA[®] is permanently discontinued for any reason, the reason will be recorded and the patient should be encouraged to remain in the registry for the full 10 years.

For patients enrolled from a prior AbbVie HUMIRA® study, ongoing events at the time of registry entry will be collected.

